7.3 Subject Population(s) for Analysis

- All-randomized population: Any subject randomized into the study, regardless of whether they received study drug. Inclusion and exclusion criteria are provided in table 1.
- All-treated population: Any subject randomized into the study that received at least one dose of study drug
- All-completed population: Only subjects who completed ALL study related procedures and follow-up will be included

8 Safety and Adverse Events

Unanticipated Problems Involving Risk to Subjects or Others (UPIRTSO)

Any unanticipated problem or adverse event that meets the following three criteria:

- Serious: Serious problems or events that results in significant harm, (which may be physical, psychological, financial, social, economic, or legal) or increased risk for the subject or others (including individuals who are not research subjects). These include: (1) death; (2) life threatening adverse experience; (3) hospitalization - inpatient, new, or prolonged; (4) disability/incapacity - persistent or significant; (5) birth defect/anomaly; (6) breach of confidentiality and (7) other problems, events, or new information (i.e. publications, DSMB reports, interim findings, product labeling change) that in the opinion of the local investigator may adversely affect the rights, safety, or welfare of the subjects or others, or substantially compromise the research data, **AND**
- Unanticipated: (i.e. unexpected) problems or events are those that are not already described as potential risks in the protocol, consent document, not listed in the Investigator's Brochure, or not part of an underlying disease. A problem or event is "unanticipated" when it was unforeseeable at the time of its occurrence. A problem or event is "unanticipated" when it occurs at an increased frequency or at an increased severity than expected.
- Related: A problem or event is "related" if it is possibly related to the research procedures.

Adverse Event

An untoward or undesirable experience associated with the use of a medical product (i.e. drug, device, biologic) in a patient or research subject.

Patients undergoing cardiac surgery with CPB sustain a multitude of adverse events as a result of their medical condition and the exposure to surgical procedure and CPB. Therefore, in order to make the safety evaluation of vitamin B12a meaningful, only selected adverse events that are medically important and/or may have a causal relationship to vitamin B12a will be collected.

Serious Adverse Event

Adverse events are classified as serious or non-serious. Serious problems/events can be well defined and include;

- death
- life threatening adverse experience
- hospitalization
- inpatient, new, or prolonged; disability/incapacity
- persistent or significant disability or incapacity
- birth defect/anomaly

and/or per protocol may be problems/events that in the opinion of the sponsor-investigator may have adversely affected the rights, safety, or welfare of the subjects or others, or substantially compromised the research data.

All adverse events that do not meet any of the criteria for serious, should be regarded as **non-serious adverse events**.

Adverse Event Reporting Period

We will monitor for all adverse events over the first 12 hours after the administration of study drug and monitor for acute kidney injury (AKI) and stroke for 72 hours after drug administration. Patients will continue to be monitored per standard ICU protocol after this point.

Preexisting Condition

A preexisting condition is one that is present at the start of the study. A preexisting condition should be recorded as an adverse event if the frequency, intensity, or the character of the condition worsens during the study period.

General Physical Examination Findings

At screening, any clinically significant abnormality should be recorded as a preexisting condition. At the end of the study, any new clinically significant findings/abnormalities that meet the definition of an adverse event will also be recorded and documented as an adverse event.

Post-study Adverse Event

All unresolved adverse events should be followed by the sponsor-investigator until the events are resolved, the subject is lost to follow-up, or the adverse event is otherwise explained.

Hospitalization, Prolonged Hospitalization or Surgery

Any adverse event that results in hospitalization or prolonged hospitalization aside from the anticipated post-surgical hospitalization should be documented and reported as a serious adverse event unless specifically instructed otherwise in this protocol. Any condition responsible for surgery should be documented as an adverse event if the condition meets the criteria for an adverse event.

Neither the condition, hospitalization, prolonged hospitalization, nor surgery are reported as an adverse event in the following circumstances:

- Hospitalization or prolonged hospitalization for diagnostic or elective surgical procedures for a preexisting condition. Surgery should not be reported as an outcome of an adverse event if the purpose of the surgery was elective or diagnostic and the outcome was uneventful.
- Hospitalization or prolonged hospitalization for therapy of the target disease of the study, unless it is a worsening or increase in frequency of hospital admissions as judged by the clinical investigator.

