3.3 Duration of Participation

Patients will be randomized and administered study drug if criteria are met within the first 24hrs after being removed from cardiopulmonary bypass. Once study drug is given, hemodynamic variables will be monitored the first 30 minutes, all adverse events will be monitored the first 12 hours and development of acute kidney injury (AKI) and stroke will be monitored for 72 hours. Data will be collected the first 7 days through the electronic medical record and at 30 days the patient will be called for follow up and assessment of 30 day mortality.

Screening/Consent

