8.1 Recording of Adverse Events

Information on all adverse events should be recorded immediately in the source document, and also in the appropriate adverse event section of the case report form (CRF). All clearly related signs, symptoms, and abnormal diagnostic, laboratory or procedure results should be recorded in the source document.

All adverse events occurring during the study reporting period must be recorded. The clinical course of each event should be followed until resolution, stabilization, or until it has been ultimately determined that the study treatment or participation is not the probable cause. Serious adverse events that are still ongoing at the end of the study period must be followed up, to determine the final outcome. Any serious adverse event that occurs during the Adverse Event Reporting Period and is considered to be at least possibly related to the study treatment or study participation should be recorded and reported immediately.

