*** Relationship Index Example**

The relationship of an AE to the Investigational Drug is a clinical decision by the sponsor-investigator (PI) based on all available information at the time of the completion of the CRF and is graded as follows:

1. Not related: a reaction for which sufficient information exists to indicate that the etiology is unrelated to the study drug; the subject did not receive the study medication or the temporal sequence of the AE onset relative to administration of the study medication is not reasonable or the event is clearly related to other factors such as the subject's clinical state, therapeutic intervention or concomitant therapy.
2. Unlikely: a clinical event, including laboratory test abnormality, with a temporal relationship to drug administration which makes a causal relationship improbable and in which other drugs, chemicals, or underlying disease provide plausible explanations.
3. Possible: a clinical event, including laboratory test abnormality, with a reasonable time sequence to administration of the drug but which could also be explained by concurrent disease or other drugs or chemicals; information on drug withdrawals may be lacking and unclear.
4. Probable: a clinical event including laboratory test abnormality, with a reasonable time sequence to administration of the drug, unlikely to be attributed to concurrent disease or other drugs or chemicals and which follows a clinically reasonable response on withdrawal (de-challenge): re-challenge information is not required to fulfill this definition.
5. Definite: a reaction that follows a reasonable temporal sequence from administration of the drug, or in which the drug level has been established in body fluids or tissues, that follows a known or expected response pattern to the suspected drug, and that is confirmed by improvement on stopping or reducing the dosage of the drug, and reappearance of the reaction on repeated exposure (re-challenge).

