8.4 Stopping Rules

In the case of anaphylaxis drug infusion will be stopped. In the event of blood pressure overshoot the Vasopressors will be titrated to stay under the upper limit blood pressure goal of the treatment team. Urine and skin discoloration is an expected side effect, there will be no change in protocol or management if this occurs.

The study drug has been used safely over a prolonged period with very few reported adverse events. We do not expect any other related adverse events.

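### Sections 8 and 8.1 give conflicting rules for collecting adverse events, and the selective rule lets a possibly unblinded causality judgement decide whether lesser events are recorded

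*Combined protocol and SAP*

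**What the plan says.** Section 8 (Adverse Event) notes that cardiac surgery with bypass produces many adverse events. To keep the safety evaluation meaningful, it states that "only selected adverse events that are medically important and/or may have a causal relationship to vitamin B12a will be collected". The sentence gives no list and no cross-reference. Section 8 defines serious events but does not define medical importance.

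Other places set no such filter:

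- Section 8.1: "Information on all adverse events should be recorded immediately in the source document, and also in the appropriate adverse event section" of the CRF, and "All adverse events occurring during the study reporting period must be recorded".
- Section 8, Adverse Event Reporting Period: "We will monitor for all adverse events over the first 12 hours after the administration of study drug", with AKI and stroke followed for 72 hours.
- Section 3.3: "all adverse events will be monitored the first 12 hours".
- The relatedness scale under Section 8.2.1 begins with "Not related: a reaction for which sufficient information exists to indicate that the etiology is unrelated to the study drug". The sponsor-investigator assigns the grade when the CRF is completed.

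On blinding, Section 8.3 assigns masking to the research pharmacy, while Section 8.4 says that "Urine and skin discoloration is an expected side effect".

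**The concern.** Two problems follow from the same sentence.

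First, the rules cannot both be followed. Take a minor event at hour 6 that nobody links to the drug. Section 8.1 requires it on the CRF, and Section 8 says it is not collected. Staff who resolve this differently will produce records that are not comparable between patients.

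Second, one of the two routes into the selective rule is a suspected link to B12a. For an event that is not medically important, that suspicion decides whether the event exists in the data at all. Adverse event counts by arm can be compared only if an event has the same chance of being recorded in each arm. A visibly discoloured patient may prompt a link to the drug, or may prompt the recorder to dismiss an event as expected. A patient without discolouration may prompt neither.

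The stake is the general safety record. Section 1.4 says that no prospective study has been done in this population, and Section 1.6 lists unknown adverse effects among the risks. A filter that depends on suspicion is weakest for effects that nobody yet suspects, and Section 8.4 says in advance that no other related events are expected. Events left off the CRF cannot be restored from it at analysis.

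**Working it through.** The plan states no figure on this point, so there is nothing to reproduce. The check is a comparison of text, followed by an illustration on assumed rates.

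**Step 1. Do the rules conflict?**

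| Place | Events covered | Filter |
|---|---|---|
| Section 8, Adverse Event | selected events, unlisted | medically important and/or possibly caused by B12a |
| Section 8.1 | all in the reporting period, in source and CRF | none |
| Sections 3.3 and 8 (Reporting Period) | all, monitored for 12 hours | none |

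The monitoring statements alone could be squared with selective collection: watch for everything, record some of it. Section 8.1 closes that route, because it requires recording in both the source document and the CRF. The not-related grade fits Section 8.1 but does not settle the matter, since a medically important event with another cause would also need that grade. The conflict rests on Section 8 against Section 8.1.

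**Step 2. Which events does the causality limb decide?**

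With the two limbs joined by and/or, the ordinary reading is that either suffices.

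- Medically important: collected, whatever the suspected cause.
- Not medically important, B12a suspected: collected.
- Not medically important, B12a not suspected: not collected.

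Suspected cause therefore decides collection only for events not deemed medically important.

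**Step 3. What lies outside the filter?**

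Section 3.6 names anaphylaxis, systolic pressure above 140 mmHg in the first 4 hours, 30-day mortality, lengths of stay, ventilator time, stroke, AKI, SOFA, new arrhythmias, mechanical support, coagulation changes and transfusion. None is defined by relatedness, and Section 3.7 takes many of them from the CRF or the medical record. The primary MAP endpoint does not use adverse event data.

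**Step 4. How large could the distortion be?**

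Let p be the true proportion of patients with a lesser event, the same in both arms, and let cB and cP be the proportions captured on B12a and placebo. Then

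apparent difference = p × cB − p × cP = p × (cB − cP).

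The documents give none of these inputs. All values below are assumptions.

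| p | cB, cP | Recorded, B12a v placebo | Apparent difference |
|---|---|---|---|
| 20%, 40% or 60% | 80%, 80% | equal | 0 points |
| 20% | 80%, 50% | 16% v 10% | 6 points |
| 40% | 80%, 50% | 32% v 20% | 12 points |
| 60% | 80%, 50% | 48% v 30% | 18 points |
| 20% | 80%, 30% | 16% v 6% | 10 points |
| 40% | 80%, 30% | 32% v 12% | 20 points |
| 60% | 80%, 30% | 48% v 18% | 30 points |

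Swapping cB and cP reverses the sign. If every event is recorded (cB = cP = 100%), the difference is 0. The distortion needs both the selective rule and capture that differs by arm. The table shows how the mechanism scales and estimates nothing about this trial.

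**The case against.** The best defence reads the Section 8 sentence as setting the scope, so that Section 8.1 means all events within that scope. There is a reason for it: these patients have many events from surgery and bypass, and recording every one could bury a drug signal. That reason is sound and supports selective collection as a design. It does not rescue the text. Section 8.1 does not refer back to a selected set, Section 8 supplies no list, and its general definition of an adverse event is broad.

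A reader might infer that the whole safety comparison depends on judged causality. The documents do not support that. Medical importance is a separate route in, and the Section 3.6 endpoints need no relatedness judgement. A reader might also infer that between-arm adverse event rates will be biased. That goes too far as well: Section 7.2 specifies no between-arm comparison of general adverse events, and nothing shows that capture would differ by arm.

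The link from discolouration to arm is also imperfect. Sections 1.2 and 5.2 allow an unblinded dose of Cyanokit in the first 4 hours, so a placebo patient could be discoloured for much of the 12-hour window. This weakens the unblinding argument without removing it.

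Finally, Section 8.2.1 limits IRB reports to directly related serious events and unanticipated problems. That governs reporting, not collection, and is no part of this conflict.

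**Conclusion.** The point holds in a limited form. Sections 8 and 8.1 give incompatible collection rules, and the documents do not reconcile them. That part rests on the text alone and is firm.

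If the selective rule is the one followed, suspected causality can decide whether an event not deemed medically important is collected, and the judgement may not be blind. General adverse event tabulations could then be biased in either direction. This part assumes that recorders act on suspicion before the event is entered and that discolouration informs some of those suspicions. The size cannot be estimated from the documents; the 0 to 30 points above follow only from assumed rates.

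The Section 3.6 safety endpoints and the primary MAP analysis stand. The text should be corrected because the contradiction is plain and the remedy is cheap, not because a biased result has been shown.

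**What to change.** Reconcile Sections 3.3, 8 (Adverse Event and Adverse Event Reporting Period) and 8.1 into one collection rule, applied identically in both arms. Either of two forms would do:

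1. Record every adverse event in the 12-hour window, keep the 72-hour follow-up for AKI and stroke, and delete the selective sentence.
2. Keep collection selective because of the expected number of surgical events, but replace the causality limb with a fixed list of event types, cross-referenced to Section 3.6, plus all serious events. Collect these irrespective of suspected cause, and amend Section 8.1 and the monitoring statements to match.

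Under either form, state that relatedness is graded only after the event has been recorded.

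The cost is protocol and CRF wording. The first form also brings some extra adverse event entry for 50 patients, which may not be trivial given how many events the protocol expects. The second form avoids most of that, but a lesser event outside the list would go uncollected in both arms alike.

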8.1 Recording of Adverse Events

Information on all adverse events should be recorded immediately in the source document, and also in the appropriate adverse event section of the case report form (CRF). All clearly related signs, symptoms, and abnormal diagnostic, laboratory or procedure results should be recorded in the source document.

All adverse events occurring during the study reporting period must be recorded. The clinical course of each event should be followed until resolution, stabilization, or until it has been ultimately determined that the study treatment or participation is not the probable cause. Serious adverse events that are still ongoing at the end of the study period must be followed up, to determine the final outcome. Any serious adverse event that occurs during the Adverse Event Reporting Period and is considered to be at least possibly related to the study treatment or study participation should be recorded and reported immediately.

8.2 Reporting of Serious Adverse Events and Unanticipated Problems

When an adverse event has been identified, the study team will take appropriate action necessary to protect the study participant and then complete the Study Adverse Event Worksheet and log. The sponsor-investigator will evaluate the event and determine the necessary follow-up and reporting required.

8.2.1 Sponsor-Investigator reporting: notifying the Mayo IRB

Monitoring activities will be performed by the PI and study team. The investigators will allocate adequate time for monitoring activities. The Investigators will also ensure that the monitor or other compliance or quality assurance reviewer is given access to all the study-related documents and study related facilities (e.g. pharmacy, diagnostic laboratory, etc.), and has adequate space to conduct the monitoring visit. A data safety monitoring board is not required by this institution.

The sponsor-investigator will report to the Mayo IRB any UPIRTSOs and NonUPIRTSOs according to the Mayo IRB Policy and Procedures and it will include the following:

- Subject's name:
- Medical record number:
- Disease/histology (if applicable):
- The date the adverse event occurred:
- Description of the adverse event:
- Relationship of the adverse event to the research (drug, procedure, or intervention*):
- If the adverse event was expected:
- The severity of the adverse event: (use a table to define severity scale 1-5**)
- If any intervention was necessary:

- Resolution: (was the incident resolved spontaneously, or after discontinuing treatment)
- Date of Resolution:

The sponsor-investigator will review all adverse event reports to determine if specific reports need to be made to the IRB and FDA. The sponsor-investigator will sign and date the adverse event report when it is reviewed. For this protocol, only directly related SAEs/UPIRTSOs will be reported to the IRB.

*** Relationship Index Example**

The relationship of an AE to the Investigational Drug is a clinical decision by the sponsor-investigator (PI) based on all available information at the time of the completion of the CRF and is graded as follows:

1. Not related: a reaction for which sufficient information exists to indicate that the etiology is unrelated to the study drug; the subject did not receive the study medication or the temporal sequence of the AE onset relative to administration of the study medication is not reasonable or the event is clearly related to other factors such as the subject's clinical state, therapeutic intervention or concomitant therapy.
2. Unlikely: a clinical event, including laboratory test abnormality, with a temporal relationship to drug administration which makes a causal relationship improbable and in which other drugs, chemicals, or underlying disease provide plausible explanations.
3. Possible: a clinical event, including laboratory test abnormality, with a reasonable time sequence to administration of the drug but which could also be explained by concurrent disease or other drugs or chemicals; information on drug withdrawals may be lacking and unclear.
4. Probable: a clinical event including laboratory test abnormality, with a reasonable time sequence to administration of the drug, unlikely to be attributed to concurrent disease or other drugs or chemicals and which follows a clinically reasonable response on withdrawal (de-challenge): re-challenge information is not required to fulfill this definition.
5. Definite: a reaction that follows a reasonable temporal sequence from administration of the drug, or in which the drug level has been established in body fluids or tissues, that follows a known or expected response pattern to the suspected drug, and that is confirmed by improvement on stopping or reducing the dosage of the drug, and reappearance of the reaction on repeated exposure (re-challenge).

**** Severity Index Example**

The maximum intensity of an AE during a day should be graded according to the definitions below and recorded in details as indicated on the CRF. If the intensity of an AE changes over a number of days, then separate entries should be made having distinct onset dates.

1. Mild: AEs are usually transient, requiring no special treatment, and do not interfere with patient's daily activities.

2. Moderate: AEs typically introduce a low level of inconvenience or concern to the patient and may interfere with daily activities, but are usually ameliorated by simple therapeutic measures.

3. Severe: AEs interrupt a patient's usual daily activity and traditionally require systemic drug therapy or other treatment.

